6.4.1. Non-Responder Imputation

A nonresponder imputation (NRI) method imputes missing values as non-responses and can be justified based on the composite strategy for handling intercurrent events (ICH E9 R1). This imputation procedure assumes the effects of treatments disappear after the occurrence of an intercurrent event defined by the associated censoring rule.

For DBLs occurring prior to final DBL, all categorical endpoints will utilize the NRI method after applying the primary censoring rule to patients who permanently discontinued study drug or were rescued (described in Section 6.4). Additionally, all primary and key secondary categorical endpoints will utilize NRI after applying the secondary censoring rule. For analyses which utilize either of the censoring methods, randomized patients without at least 1 postbaseline observation will also be defined as non-responders for all visits. In addition, patients who are missing a value prior to discontinuation or rescue (if censoring on rescue) (ie, the patient is missing an intermediate visit) will be imputed as non-responders at that visit.

For the final DBL, the categorical endpoints will be summarized by observed and mLOCF data, and no NRI will be applied.

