4.2.3. Other Secondary Objectives for Week 16 Responders

The secondary objectives and corresponding endpoints for those who responded at Week 16 and continue in the study beyond 16 weeks are as follows:

Objective	Endpoint
To describe the long-term efficacy of baricitinib 1-mg QD or 2-mg QD in AD as measured by improvement in signs and symptoms of AD	
 Proportion of patients with a response of Investigator's Global Assessment (IGA) 0 or 1 at Week 16 who maintain an IGA 0 or 1 at Weeks 28, 40, 52, 64, 76, 88 and 104 Proportion of patients with a response of IGA 0 or 1 at Week 16 who achieve Eczema Area and Severity Index score (EASI75) assessed at Weeks 28, 40, 52, 64, 76, 88 and 104 Proportion of patients with a response of IGA 0 or 1 at Week 16 who achieve SCORing Atopic Dermatitis (SCORAD75) at Weeks 28, 40, 52, 64, 76, 88 and 104 Mean percent change from baseline in EASI score at Weeks 28, 40, 52, 64, 76, 88 and 104 Mean percent change from baseline in SCORAD score at Weeks 28, 40, 52, 64, 76, 88 and 104 Mean percent change from baseline in SCORAD pruritus at Weeks 28, 40, 52, 64, 76, 88 and 104 Mean percent change from baseline in Patient Oriented Eczema Measure (POEM) at Weeks 28, 40, 52, 64, 76, 88 and 104

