5. Study Design

Study I4V-MC-JAIW (JAIW) is a multicenter, randomized, double-blind, placebo-controlled, parallel-group, outpatient Phase 3 study evaluating the efficacy and safety of baricitinib 1-mg QD and 2-mg QD as compared to placebo in adult patients with moderate to severe AD. The study is divided into 3 periods: a 5-week Screening Period, a 104-week Double-Blinded Treatment Period, and a 4-week Post-Treatment Follow-Up Period.

Approximately 450 patients aged ≥ 18 years who have responded inadequately to or who are intolerant of topical therapy will be randomized at a 1:1:1 ratio to receive placebo QD, baricitinib 1-mg QD, or baricitinib 2-mg QD (approximately 150 patients per group). Patients will be stratified at randomization according to disease severity (IGA 3 versus 4).

The primary and key secondary endpoints are assessed prior to or at Visit 8 (Week 16). At Week 16 those patients who met IGA 0 or 1 and who have not required rescue therapy prior to Week 16 will be allowed to continue in this study. All other patients will be discontinued from this study and may be eligible to enroll in a separate open-label study (Study JAIX). Patients experiencing worsening in disease severity resulting in an IGA score of ≥ 3 after Week 16 of Study JAIW will also have to be discontinued from this study and may be eligible to enroll in the open-label Study JAIX. Patients who complete Week 104 (Visit 15) will have the option to transition to open-label Study JAIX, if eligibility criteria are met regardless of responder status, or continue to the post-treatment follow-up.

Figure JAIW.5.1 illustrates the study design.

Abbreviations: AD = atopic dermatitis; QD = once daily; V = visit; W = week.

- ^a At Week 16, all patients who achieve an IGA 0 or 1 and who have not required rescue therapy before Week 16 will be allowed to continue in this study. All other patients will be discontinued from this study and may be eligible to enroll in the separate open-label Study JAIX.
- ^b Patients who complete this study will be eligible for assessment to enroll in open-label Study JAIX.
- ^c Occurs approximately 28 days after the last dose of investigational product.

Figure JAIW.5.1. Illustration of study design for I4V-MC-JAIW.

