6.2.2. Analysis Populations

Intent-to-treat (ITT) population: The ITT population analysis set is defined as all randomized patients.

Per-protocol set (PPS) population: The PPS of the ITT population analysis set will include those patients who do not have any identified important protocol violations considered to impact efficacy analyses. Qualifications for and identification of significant or important protocol violations will be determined while the study remains blinded, prior to database lock.

Unless otherwise specified, the efficacy and health outcome analyses will be conducted on the ITT population (Gillings and Koch 1991), which seeks to preserve the benefits of randomization and avoid the issue of selection bias. Patients will be analyzed according to the treatment to which they were randomized. In addition, the primary will be repeated using the PPS population.

W16 Responders population: The W16 responders analysis set is defined as patients who met IGA 0 or 1, have not required rescue therapy prior to Week 16, and continue in the study beyond 16 weeks.

Efficacy will be summarized in 2 efficacy analysis sets:

- Weeks 0 to 16 based on ITT population, and
- after Week 16 to Week 104 based on W16 Responders population.

The long-term summary will include up to 104 weeks. By design all patients continuing past Week 16 of JAIW were responders without rescue mediation. As it is assumed there will be few placebo responders continuing past Week 16, long-term efficacy will be characterized using descriptive statistics after Week 16 up to Week 104 in the final database lock (DBL)

Safety population: The safety population is defined as all randomized patients who receive at least 1 dose of investigational product and who did not discontinue from the study for the reason 'Lost to Follow-up' at the first postbaseline visit. This definition excludes patients with no safety assessments postbaseline so that incidence rates are not underestimated.

Safety analyses will be done using the safety population. Patients will be analyzed according to the treatment regimen to which they were assigned. Analyses of the safety endpoints, many of which are incidence based, will include all patients in the safety population, unless specifically stated otherwise.

The following are the treatment groups for the analysis of safety for Study JAIW for the 16-week interim analyses:

Treatment Group	Definition

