Fisher's exact test will be used to test the difference between each baricitinib dose and placebo in proportion of patients experiencing adverse events (AEs), discontinuation from study drug, and other categorical safety data. Continuous vital signs, body weight, and other continuous safety variables, including laboratory variables, will be analyzed by an ANCOVA with treatment group and baseline value in the model. The significance of within-treatment group changes from baseline will be evaluated by testing whether or not the treatment group LSM changes from baseline are different from zero; the standard error for the LSM change will also be displayed. Differences in LSM will be displayed, with the p-value associated with the LSM comparison to placebo and a 95% CI on the LSM difference also provided. In addition to the LSMs for each group, the within-group p-value for the change from baseline will be displayed.

Time to event will be analyzed using cumulative incidence function with observed values, defining first time reaching the event IGA (0,1), EASI 75, or Itch NRS 4-pt improvement before rescue as onset, treating rescue and discontinuing for lack of efficacy as competing event censor up to Week 16.

For final database lock, the main analysis method for efficacy and health outcomes variables will use descriptive summary per observed and mLOCF data.

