Table JAIW.6.1 summarizes how imputation techniques and censoring rules are applied to efficacy and health outcome endpoints.

Table JAIW.6.1. Imputation Techniques for Various Variables

Efficacy and Health Outcome Endpoints	Imputation Method
IGA(0,1), EASI75, 4-point Itch NRS improvement	NRI ^{ab} , pMI ^a , Tipping point ^a , mLOCF
EASI90, SCORAD75	NRI ^{ab} , pMI ^a
EASI percent change, ADSS Item 2 change, Skin Pain NRS change	MMRM ^{ab} , mLOCF ^a , pMI ^a , mBOCF ^a
All remaining categorical measures	NRI ^a , mLOCF
All remaining continuous efficacy and health outcome measures in secondary analysis	MMRM ^a , mLOCF ^a
All continuous efficacy and health outcome measures in exploratory analysis	MMRM ^a

Abbreviations: AD = atopic dermatitis; ADSS = Atopic Dermatitis Sleep Scale; EASI = Eczema Area and Severity Index score; IGA = Investigator's Global Assessment for AD; mBOCF = baseline observation carried forward; mLOCF = modified last observation carried forward; MMRM = mixed model repeated measures; NRI = nonresponder imputation, NRS = Numeric Rating Scale; pMI = placebo multiple imputation; SCORAD = SCORing Atopic Dermatitis.

- a Analyses utilizing the primary censoring rule.
- b Analyses utilizing the secondary censoring rule.

Tipping Point, pMI, NRI, and MMRM (etc.) were used in the Week 16 interim DBL. The Final DBL only use observed and mLOCF.

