6.4.3. Modified Last Observation Carried Forward

For continuous and categorical measures, a mLOCF imputation technique replaces missing data with the most recent nonmissing postbaseline assessment. The specific modification to the LOCF is data after an intercurrent event will not be carried forward thus the mLOCF is applied after the specified censoring rule is implemented. The mLOCF assumes the effect of treatment remain the same after the event that caused missing data as it was just prior to the missing data event. Analyses using mLOCF require a nonmissing baseline and at least 1 postbaseline measure otherwise the data is missing for analyses purposes. Analyses using mLOCF help ensure the number of randomized patients who were assessed postbaseline is maximized and is reasonable for this data as data directly prior to an intercurrent event (such as initiation of rescue therapy or drop out) is likely a non-efficacious response.

All continuous efficacy and health outcomes key secondary and secondary endpoints will use mLOCF imputation methodology with an ANCOVA as sensitivity analyses to the MMRM analyses.

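### At the final lock, maintenance of response is summarised only by observed and mLOCF data, so no planned figure shows the low side for Week 16 responders who leave for reasons other than relapse

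*SAP*

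**What the plan says.** Section 4.2.3 sets descriptive long-term objectives. The first is the proportion of Week 16 IGA 0/1 responders "who maintain an IGA 0 or 1 at Weeks 28, 40, 52, 64, 76, 88 and 104"; the next two are the proportions of the same patients with EASI75 and with SCORAD75 at those weeks.

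Section 6.2.2 fixes the set: "The W16 responders analysis set is defined as patients who met IGA 0 or 1", had no rescue before Week 16, and continue beyond it. Section 5 adds that patients who worsen to IGA 3 or more "after Week 16 of Study JAIW will also have to be discontinued from this study".

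For the final lock, Section 6.2.4 says "the main analysis method for efficacy and health outcomes variables will use descriptive summary per observed and mLOCF data". The note under Table JAIW.6.1 says "The Final DBL only use observed and mLOCF". Section 6.4.1 says "For the final DBL, the categorical endpoints will be summarized by observed and mLOCF data, and no NRI will be applied". Section 6.4 excludes data collected after permanent discontinuation of study drug.

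Section 6.4.3 has mLOCF replace a missing value by the latest non-missing postbaseline one. It calls this reasonable because "data directly prior to an intercurrent event (such as initiation of rescue therapy or drop out) is likely a non-efficacious response".

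**The concern.** The question in Section 4.2.3 concerns all Week 16 responders at each later visit. Because relapse forces exit, the observed proportion counts a relapser at most at the visit where the relapse is recorded, and at no later visit. It answers how many of those still in the study are responding.

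mLOCF keeps essentially every Week 16 responder in the denominator, since the Week 16 value is itself postbaseline. It also carries a recorded IGA of 3 or more forward as a non-response. What it leaves open is the other leavers. Everyone enters with IGA 0/1, and IGA 3 or more is the relapse exit, so a patient who leaves for another reason normally leaves with IGA 0 to 2, most often 0 or 1. A patient never assessed after Week 16 is carried as a responder to Week 104. The rationale in Section 6.4.3 suits Weeks 0 to 16 but not these patients.

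A narrower gap concerns exit values. Section 6.2 maps early-termination data to a visit only if they fall within the visit window. Section 6.2.3 gives a window of ±4 days for unscheduled assessments. The long-term visits are 12 weeks apart (16 weeks for the last), so an exit assessment can easily fall outside every window. The allowance in Section 6.2 for unscheduled data in mLOCF names change from baseline, not categorical response. Section 6.4.3 points towards inclusion but does not settle it. At stake is a picture of durability that is one-sided for these leavers.

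**Working it through.** The SAP gives no relapse, exit or maintenance rate, so there is no figure of its own to reproduce. The directions follow from its rules; the sizes below rest on assumed rates and cover IGA 0/1 only.

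**Identity.** Among all Week 16 responders, at a given visit:
- NRI = share with IGA 0/1 now.
- mLOCF = share with IGA 0/1 now + share who left for other reasons with last value IGA 0/1.
- Observed = share with IGA 0/1 now ÷ share assessed at that visit.

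So mLOCF − NRI is the share of non-relapse leavers whose last value was IGA 0/1, however many relapses are recorded.

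**Chain.** All start in IGA 0/1 and pass seven visits (Weeks 28 to 104). At each visit a patient is at IGA 0/1, at IGA 2, at IGA ≥ 3 (recorded on drug, then out), or has left for another reason. Assumed weights (to IGA 0/1 : to IGA 2 : relapse):
- Base: 70:12:10 from IGA 0/1; 35:25:32 from IGA 2.
- Milder: 80:8:6 and 40:30:24.

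The weights are rescaled to 1 minus the other-exit rate per interval (0%, 2% or 4%, equal from both states).

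**First steps (base, 2%).**
- Week 28: IGA 0/1 = 0.98 × 70/92 = 0.7457; IGA 2 = 0.98 × 12/92 = 0.1278.
- Week 40: IGA 0/1 = 0.7457 × 0.7457 + 0.1278 × (0.98 × 35/92) = 0.6037.
- Week 104: IGA 0/1 = 0.2363; assessed = 0.3422; other exits with last value IGA 0/1 = 0.0778.
- Observed = 0.2363/0.3422 = 69.1%; mLOCF = 0.2363 + 0.0778 = 31.4%; NRI = 23.6%.

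**Week 104 results.**

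| Case | Other exits per interval | Observed | mLOCF | NRI | Assessed |
|---|---|---|---|---|---|
| Base | 0% | 69.1% | 27.2% | 27.2% | 39.4% |
| Base | 2% | 69.1% | 31.4% | 23.6% | 34.2% |
| Base | 4% | 69.1% | 35.3% | 20.5% | 29.6% |
| Milder | 0% | 79.8% | 47.6% | 47.6% | 59.7% |
| Milder | 2% | 79.8% | 50.9% | 41.3% | 51.8% |
| Milder | 4% | 79.8% | 53.9% | 35.8% | 44.9% |

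With relapse as the only exit, mLOCF equals NRI, so the correction for recorded relapses is complete. About 87% (base) or 91% (milder) of values carried forward for other exits are IGA 0/1. If other exits are twice as likely from IGA 2, these shares fall to about 77% and 83%, and the Week 104 pairs barely move (base 31.0/23.3 and 34.7/19.9; milder 50.5/40.9 and 53.1/35.1).

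**Against the 0% row** (which supposes leavers would have behaved like stayers in the same state), mLOCF errs by +4.2 and +8.1 points and NRI by −3.6 and −6.8 in the base case. In the milder case the errors are +3.3 and +6.3 against −6.3 and −11.8.

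**Uncaptured relapses.** In a simpler one-step illustration, take 40% relapse exits, 20% other exits (70% of them last at IGA 0/1), and 80% of those remaining at IGA 0/1. mLOCF = 0.40 × 0.80 + 0.20 × 0.70 = 46%. If a quarter of relapse values do not enter and IGA 0/1 is carried instead, add 0.40 × 0.25 = 10 points, giving 56%.

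**The case against.** The strongest reply is that the largest contrast is already on show. A reader might infer from 69% against 27% that the plan overstates durability by some 40 points. The document does not support that: observed and mLOCF are required together, and nothing makes observed the headline. Only the gap between mLOCF and NRI is unseen. This stands.

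Second, the analyses are descriptive, Table JAIW.6.5 labels them exploratory, and Section 6.7 tabulates disposition after Week 16. This also stands and limits the grade, though disposition does not give response at each visit.

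Third, calling mLOCF high presupposes an estimand, and the SAP sets none after Week 16. Read as response while on treatment, the last on-drug value is not high. That is fair, and it argues for showing two figures rather than replacing one with the other.

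Fourth, a reader might conclude that mLOCF ought to be named the lead because it lies nearer the truth. The illustration does not bear that out: NRI is closer in the base case and mLOCF in the milder one.

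Fifth, entry and forced exit are defined by IGA. An exit at IGA 3 or more need not be an EASI75 or SCORAD75 non-response, so the sizes do not transfer to those endpoints.

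Last, the Table JAIW.6.1 row for "EASI90, SCORAD75" lacks mLOCF while Table JAIW.6.5 plans it for SCORAD75. One might infer that mLOCF is not intended there, but the note under Table JAIW.6.1 settles the intent, so this is editorial.

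**Conclusion.** The point holds at minor grade. The observed summary describes only those still in the study. mLOCF largely corrects for relapses recorded on drug, fully so for IGA 0/1. For other leavers it mostly carries a response forward on a rationale that does not fit a responder set, and no planned summary shows the opposite side.

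In the illustration the unseen gap at Week 104 is about 8 to 15 points (31% against 24% to 35% against 20%), or 10 to 18 points in the milder case (51% against 41% to 54% against 36%). These sizes depend on assumed exit rates and on relapses being recorded on drug, and they apply to IGA 0/1 only. For EASI75 and SCORAD75 the effect of a relapse exit depends on the value at exit. No hypothesis test, alpha allocation or Week 16 result is affected.

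**What to change.** 1. In Section 6.4.1, replace the exclusion of NRI at the final lock with a supplementary descriptive NRI summary over all Week 16 Responders for IGA 0/1, EASI75 and SCORAD75 at Weeks 28 to 104. Show it beside mLOCF as the lower and upper figures for non-relapse exits. Align Section 6.2.4 and the note under Table JAIW.6.1, and say that the observed proportion is not to be presented alone as maintenance of response.
2. In Section 6.4.3, state that the last on-treatment assessment enters the categorical mLOCF, including an early-termination value outside the visit window.
3. As an editorial alignment, add mLOCF for SCORAD75 in Table JAIW.6.1.

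The cost is a few sentences, one table cell and three extra descriptive displays using the NRI method already applied at the Week 16 lock. The downside is less favourable maintenance figures. NRI also errs low for responders who leave for unrelated reasons, so it should remain supplementary.

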6.4.2. Mixed Model for Repeated Measures

Mixed model for repeated measures analyses will be performed on continuous endpoints to mitigate the impact of missing data. This approach assumes missing observations are missing-at-random (missingness is related to observed data) and borrows information from patients in the same treatment arm taking into account both the missingness of data through the correlation of the repeated measurements.

Essentially MMRM estimates the treatment effects had all patients remained on their initial treatment throughout the study. For this reason, the MMRM imputation implies a different estimand (hypothetical strategy [ICH E9 R1]) than the one used for NRI on categorical outcomes.

All continuous endpoints will utilize MMRM after applying the primary censoring rule. As sensitivity analyses, all key secondary continuous endpoints will also utilize MMRM after applying the secondary censoring rule ([Table JAIW.6.1](#)).

6.4.3. Modified Last Observation Carried Forward

For continuous and categorical measures, a mLOCF imputation technique replaces missing data with the most recent nonmissing postbaseline assessment. The specific modification to the LOCF is data after an intercurrent event will not be carried forward thus the mLOCF is applied after the specified censoring rule is implemented. The mLOCF assumes the effect of treatment remain the same after the event that caused missing data as it was just prior to the missing data event. Analyses using mLOCF require a nonmissing baseline and at least 1 postbaseline measure otherwise the data is missing for analyses purposes. Analyses using mLOCF help ensure the number of randomized patients who were assessed postbaseline is maximized and is reasonable for this data as data directly prior to an intercurrent event (such as initiation of rescue therapy or drop out) is likely a non-efficacious response.

All continuous efficacy and health outcomes key secondary and secondary endpoints will use mLOCF imputation methodology with an ANCOVA as sensitivity analyses to the MMRM analyses.

6.4.4. Modified Baseline Observation Carried Forward

A baseline observation analysis is performed by carrying forward the baseline assessment for the continuous measures, assuming that effect of treatment will loss and patient status will return to the baseline status after the occurrence of the intercurrent event (after application of the primary censoring rule). After mBOCF imputation, data from patients with nonmissing baseline will be included in the analyses. These mBOCF analyses will be applied to ITT population and on key secondary continuous efficacy and health outcomes endpoints.

6.4.5. Placebo Multiple Imputation

The Placebo Multiple Imputation (pMI) methodology will be used as a sensitivity analysis for the analysis of the EASI75 efficacy endpoint as well as the key secondary endpoints at Week 16. In these sensitivity analyses the primary censoring rule will be applied.

The pMI assumes that the statistical behavior of drug- and placebo-treated patients after the occurrence of intercurrent events will be the same as if patients are treated with placebo. Thus, in the effectiveness context, pMI assumes no pharmacological benefit of the drug after the occurrence of intercurrent events but is a more conservative approach than mLOCF because it accounts for uncertainty of imputation, and therefore does not underestimate standard errors, and it limits bias. In the efficacy context, pMI is a specific form of a missing not at random analysis expected to yield a conservative estimate of efficacy.

In the pMI analysis, multiple imputations are used to replace missing outcomes (for drug- and placebo-treated patients who have an intercurrent event using multiple draws from the posterior predictive distribution estimated from the placebo arm. The binary outcomes will then be derived from the imputed data.

Data are processed sequentially by repeatedly calling SAS® PROC MI to impute missing outcomes at visits $t=1, \dots, T$.

1. *Initialization:* Set $t=0$ (baseline visit)
2. *Iteration:* Set $t=t+1$. Create a data set combining records from drug- and placebo-treated patients with columns for covariates \mathbf{X} and outcomes at visits $1, \dots, t$ with outcomes for all drug-treated patients set to missing at visit t and set to observed or imputed values at visits $1, \dots, t-1$.
3. *Imputation:* Run Bayesian regression in SAS® PROC MI on this data to impute missing values for visit t using previous outcomes for visits 1 to $t-1$ and baseline covariates. Note that only placebo data will be used to estimate the imputation model since no outcome is available for drug-treated patients at visit t .
4. Replace imputed data for all drug-treated patients at visit t with their observed values, whenever available up to permanent study drug discontinuation and/or rescue (if censoring on rescue). If $t < T$ then go to Step 2; otherwise, proceed to Step 5.

Repeat steps 1-4, m times with different seed values to create m imputed complete data sets.

Analysis: For continuous endpoints, fit its treatment response model (MMRM) for each completed data set. For the primary and secondary key efficacy endpoints of EASI75, IGA(0,1), EASI90, SCORAD75, and 4-point improvement from baseline in Itch NRS, the binary outcomes will be derived from the imputed data for each patient before fitting into the analysis model. A logistic regression model will be applied. For continuous endpoints, fit its treatment response model (MMRM) for each completed data set. For the primary and secondary key efficacy endpoints of EASI75, IGA(0,1), EASI90, SCORAD75, and 4-point improvement from baseline in Itch NRS, the binary outcomes will be derived from the imputed data for each patient before fitting into the analysis model. A logistic regression model will be applied.

The number of imputed data sets will be $m=100$ and a 6-digit seed value will be pre-specified for each analysis. Within the program, the seed will be used to generate the m seeds needed for imputation. The initial seed values are given in [Table JAIW.6.2](#).

Table JAIW.6.2. Seed Values for Multiple Imputation

Analysis	Seed Value
Proportion of patients achieving IGA of 0 or 1 with a ≥ 2 -point improvement from baseline at Week 16, using the primary censoring rule	123450
Percent change from baseline in EASI score at 16 weeks using the primary censoring rule. EASI75 and EASI90 will leverage imputation from EASI and therefore do not need a new seed number.	123451
Proportion of patients achieving SCORAD75 at 16 weeks using the primary censoring rule, with data up to rescue	123452
Proportions of patients achieving a 4-point improvement from baseline in Itch NRS at Week 16, using the primary censoring rule	123453
Mean change from baseline in Skin Pain NRS at Week 16 using the primary censoring rule	123454
Mean change from baseline in the score of Item 2 of the ADSS at Week 16 using the primary censoring rule	123455

Abbreviations: AD = atopic dermatitis; ADSS = Atopic Dermatitis Sleep Scale; EASI = Eczema Area and Severity Index score; IGA = Investigator's Global Assessment for AD; NRS = Numeric Rating Scale; SCORAD = SCORing Atopic Dermatitis.

The final inference on treatment difference is conducted from the multiple datasets using Rubin's combining rules, as implemented in SAS® PROC MIANALYZE.

